3.3 Clinic Stakeholder (Surgeons and Clinic Staff) Eligibility Criteria

3.3.1 Breast surgeon(s) and nursing staff, medical assistant, or mid-level provider at each participating clinic who participates in the care of patients newly diagnosed with breast cancer.

3.4 Institutional Eligibility

The study will utilize the National Cancer Institute Oncology Research Program (NCORP).¹⁹ Eligible clinics will serve a high proportion of socioeconomically disadvantaged patients, defined using two data sources. Figure 5 demonstrates the overlap between NCORP sites (represented as circles on the map) and U.S. neighborhoods designated as the most disadvantaged according to the ADI.⁵⁹ Using the 2015 NCORP Landscape Assessment, we have also identified 25 sites that report a high proportion of patients with Medicaid insurance (25-50%).

3.4.1 Using these data, 10 clinics that annually provide surgical care for 120-300 patients newly diagnosed with breast cancer will be selected to participate in this study.

3.4.2 Surgeons at eligible clinics must consent to the study as a requirement for site participation.

4.0 PATIENT REGISTRATION

4.1 CTEP/DCP Registration Procedures

Food and Drug Administration (FDA) regulations and National Cancer Institute (NCI) policy require all individuals contributing to NCI-sponsored trials to register and renew their registration annually. To register, all individuals must obtain a Cancer Therapy Evaluation Program (CTEP) Identity and Access Management (IAM) account at [REDACTED] In addition, persons with a registration type of Investigator (IVR), Non-Physician Investigator (NPIVR), or Associate Plus (AP) must complete their annual registration using CTEP's web-based Registration and Credential Repository (RCR) at [REDACTED]

RCR utilizes five person registration types.

- IVR — MD, DO, or international equivalent;
- NPIVR — advanced practice providers (e.g., NP or PA) or graduate level researchers (e.g., PhD);
- AP — clinical site staff (e.g., RN or CRA) with data entry access to CTSU applications such as the Roster Update Management System [RUMS], OPEN, Rave, acting as a primary site contact, or with consenting privileges;
- Associate (A) — other clinical site staff involved in the conduct of NCI-sponsored trials; and
- Associate Basic (AB) — individuals (e.g., pharmaceutical company employees) with limited access to NCI-supported systems.

RCR requires the following registration documents:

Documentation Required	IVR	NPIVR	AP	A	AB
FDA Form 1572	✓	✓			
Financial Disclosure Form	✓	✓	✓		
NCI Biosketch (education, training, employment, license, and certification)	✓	✓	✓		
GCP training	✓	✓	✓		
Agent Shipment Form (if applicable)	✓				
CV (optional)	✓	✓	✓		

An active CTEP-IAM user account and appropriate RCR registration is required to access all CTEP and Cancer Trials Support Unit (CTSU) websites and applications. In addition, IVRs and NPIVRs must list all clinical practice sites and Institutional Review Boards (IRBs) covering their practice sites on the FDA Form 1572 in RCR to allow the following:

- Addition to a site roster;
- Assign the treating, credit, consenting, or drug shipment (IVR only) tasks in OPEN;
- Act as the site-protocol Principal Investigator (PI) on the IRB approval

Additional information is located on the CTEP website at [REDACTED] For questions, please contact the RCR Help Desk by email at [REDACTED]

4.2 CTSU Registration Procedures

This study is supported by the NCI Cancer Trials Support Unit (CTSU).

IRB Approval

For CTEP and Division of Cancer Prevention (DCP) studies open to the National Clinical Trials Network (NCTN) and NCI Community Oncology Research Program (NCORP) Research Bases after March 1, 2019, all U.S.-based sites must be members of the NCI Central Institutional Review Board (NCI CIRB). In addition, U.S.-based sites must accept the NCI CIRB review to activate new studies at the site after March 1, 2019. Local IRB review will continue to be accepted for studies that are not reviewed by the CIRB, or if the study was previously open at the site under the local IRB. International sites should continue to submit Research Ethics Board (REB) approval to the CTSU Regulatory Office following country-specific regulations.

Sites participating with the NCI CIRB must submit the Study Specific Worksheet for Local Context (SSW) to the CIRB using IRBManager to indicate their intent to open the study locally. The NCI CIRB's approval of the SSW is automatically communicated to the CTSU Regulatory Office, but sites are required to contact the CTSU Regulatory Office at [REDACTED] to establish site preferences for applying NCI CIRB approvals across their Signatory Network. Site preferences can be set at the network or protocol level. Questions about establishing site preferences can be addressed to the CTSU Regulatory Office by email or calling [REDACTED]

In addition, the Site-Protocol Principal Investigator (PI) (i.e. the investigator on the IRB/REB approval) must meet the following criteria in order for the processing of the IRB/REB approval record to be completed:

- Holds an active CTEP status;
- Rostered at the site on the IRB/REB approval (applies to US and Canadian sites only) and on at least one participating roster;
- If using NCI CIRB, rostered on the NCI CIRB Signatory record;
- Includes the IRB number of the IRB providing approval in the Form FDA 1572 in the RCR profile; and
- Holds the appropriate CTEP registration type for the protocol.

Additional Requirements

Additional requirements to obtain an approved site registration status include:

- An active Federal Wide Assurance (FWA) number;
- An active roster affiliation with the Lead Protocol Organization (LPO) or a Participating Organization (PO); and
- Compliance with all protocol-specific requirements (PSRs).

4.2.1 Downloading Site Registration Documents

Download the site registration forms from the protocol-specific page located on the CTSU members' website. Permission to view and download this protocol and its supporting documents is restricted based on person and site roster assignment. To participate, the institution and its associated investigators and staff must be associated with the LPO or a

Protocol Organization (PO) on the protocol. One way to search for a protocol is listed below.

- Log in to the CTSU members' website ([\[REDACTED\]](#) using your CTEP-IAM username and password;
- Click on *Protocols* in the upper left of the screen
 - Enter the protocol number in the search field at the top of the protocol tree; or
 - Click on the By Lead Organization folder to expand, then select *Alliance*, and protocol number *A231701CD*.
- Click on *Documents*, select *Site Registration*, and download and complete the forms provided. (Note: For sites under the CIRB, IRB data will load automatically to the CTSU.)

4.2.2 Submitting Regulatory Requirements

Submit required forms and documents to the CTSU Regulatory Office using the Regulatory Submission Portal on the CTSU website.

To access the Regulatory Submission Portal log in to the CTSU members' website, go to the Regulatory section and select Regulatory Submission.

Institutions with patients waiting that are unable to use the Regulatory Submission Portal should alert the CTSU Regulatory Office immediately at [\[REDACTED\]](#) in order to receive further instruction and support.

4.2.3 Checking Site's Registration Status

Site registration status may be verified on the CTSU members' website.

- Click on Regulatory at the top of the screen;
- Click on Site Registration; and
- Enter the sites 5-character CTEP Institution Code and click on Go.
 - Additional filters are available to sort by Protocol, Registration Status, Protocol Status, and/or IRB Type.

Note: The status shown only reflects institutional compliance with site registration requirements as outlined within the protocol. It does not reflect compliance with protocol requirements for individuals participating on the protocol or the enrolling investigator's status with NCI or their affiliated networks.

4.2.4 Limited access information

This is a limited access study. All participating institutions will be selected by the study team per [Section 3.4](#) prior to study activation.

4.3 Patient and Clinic Stakeholder Registration Requirements

- **Patient informed consent:** Patients must willingly consent after being informed of the study activities: alternatives, potential benefits, potential risks, and discomforts. Current human protection committee approval of this protocol and a consent form is required prior to patient consent and registration. Written consent is for two surveys and the audio recording of the surgical consult.

- **Surgeon informed consent:** Participating surgeons must willingly consent after being informed of the study activities: alternatives, potential benefits, potential risks, and discomforts. Current human protection committee approval of this protocol and a consent form is required prior to surgeon consent and registration. Written consent is for participation in site implementation activities, allowing their patients to receive the decision aid, baseline survey, and audio-recording of the surgical consult.
- **Waivers of consent:** For all patient interviews and patient and clinic stakeholder focus groups, we request a waiver of documentation of informed consent for participation given the low risk nature of the study activity. Participants in each of these activities will be provided with written information describing the research, their participation, the risks, possible benefits, and all other required elements of informed consent. See [Section 13.0](#).
- **Patient- and surgeon-completed booklets:** Patient and surgeon questionnaire booklets are to be ordered prior to the registration of any patients or surgeons. Booklets can be ordered by downloading and completing the CTSU Supply Request Form, located on the CTSU Forms webpage under the Resources tab. The form must be submitted via the Regulatory Submission Portal on the CTSU website, located under the Regulatory tab. Samples of the booklets are found in Appendices I-VI, which are to be used for reference and IRB submission only. They are not to be used for patient completion.

Protected Health Information:

- Audio-recording of the consultation, interviews, and focus groups will be shared with the University of Wisconsin (UW). Although PHI will not be intentionally sent to UW, it is possible that PHI will be shared through the audio-recordings. All audio-recordings will be transcribed in full. Study staff members or outside contractors with a business associate agreement who have been approved by UW Legal Services/Privacy Officer for HIPAA compliance will be used for transcription. Although identifying information may exist on the audio files, transcriptionists will strip all identifying information once transcribed and will only have access to the subject ID that is assigned by study staff (no access to the patient-subject log or other identifying information). The de-identified transcripts will be used in data analysis by the research team. After data analysis is complete and manuscripts have been accepted for publication, the audio recordings will be destroyed and the de-identified transcripts will be stored indefinitely on a secure server.
- In order to facilitate completion of the Follow-up Survey, patients' email addresses will be entered into the Alliance database. This information will be used only by a web service to send the link for the follow-up survey. In addition, patients' zip +4 will be entered into the Alliance database (see [Section 10.1.4.4](#)).

4.4 Institutional Randomization

Prior to study activation, each of the 10 participating surgery clinics will be randomly assigned to a time when the clinic crosses over from usual care to intervention. To avoid anticipatory effects, clinics will be blinded to crossover time until the point of implementation. See [Section 4.7](#) for a description of the stratification factors for this study.

Wave	1	2	3	4	5	6	7
Clinics 9-10							
Clinics 7-8							
Clinics 5-6							
Clinics 3-4							
Clinics 1-2							
Usual care group		Implementation period (no data collection)		Intervention group			

Figure 4. Stepped-wedge study design. The effect of the decision aid on patient engagement will be evaluated as a pre/post comparison through the stepped wedge design (years 1-2). Persistent barriers to engagement will be characterized through one-on-one patient interviews (years 2-4). Stakeholder focus groups will inform the identification of targets for adjunct interventions (years 4-5).

4.5 Surgeon Registration

Surgeons will be identified during the site selection process. Following local IRB approval of this study, surgeons will be consented to participate in site implementation activities, baseline survey, and audio recording of the surgical consult.

The Surgeon Enrollment Form should then be completed and submitted to Alliance Registration Office via fax [REDACTED] or email [REDACTED]. The registration office will register the surgeon(s) to the study and send confirmation to the site via email within 1 business day. (Note: Surgeon(s) will **not** be registered to this study using OPEN.)

4.6 Patient Registration Procedures

The Oncology Patient Enrollment Network (OPEN) is a web-based registration system available on a 24/7 basis. OPEN is integrated with CTSU regulatory and roster data and with the LPOs registration/randomization systems or the Theradex Interactive Web Response System (IWRS) for retrieval of patient registration/randomization assignment. OPEN will populate the patient enrollment data in NCI's clinical data management system, Medidata Rave.

Requirements for OPEN access:

- A valid CTEP-IAM account;
- To perform enrollments or request slot reservations: Must be on an LPO roster, ETCTN corresponding roster, or participating organization roster with the role of Registrar. Registrars must hold a minimum of an Associate Plus (AP) registration type; and
- Have an approved site registration for the protocol prior to patient enrollment.

To assign an Investigator (IVR) or Non-Physician Investigator (NPIVR) as the treating, crediting, consenting, drug shipment (IVR only), or receiving investigator for a patient transfer in OPEN, the IVR or NPIVR must list the IRB number used on the site's IRB approval on their

Form FDA 1572 in RCR. If a DTL is required for the study, the IVR or NPIVR must be assigned the appropriate OPEN-related tasks on the DTL.

Prior to accessing OPEN, site staff should verify the following:

- Patient has met all eligibility criteria within the protocol stated timeframes; and
- All patients have signed an appropriate consent form and HIPAA authorization form (if applicable).

Note: The OPEN system will provide the site with a printable confirmation of registration and treatment information. You may print this confirmation for your records.

Access OPEN at [REDACTED] or from the OPEN link on the CTSU members' website. Further instructional information is in the OPEN section of the CTSU website at [REDACTED] For any additional questions, contact the CTSU Help Desk at [REDACTED]

4.7 Stratification Factors and Treatment Assignments

4.7.1 Stratification

The randomization routine is found in Section 12.0 (Statistical Considerations). Randomization occurs at the clinic practice site level only. Patient level stratification is not considered in this study.

There is one planned composite stratification factor with two levels (group 1; group 2). When assigning sites to a group, the primary factor considered was whether the site was a minority/underserved NCORP site. Sites will be stratified as follows:

Group 1: Wisconsin NCORP, Montana Cancer Consortium NCORP, Bay Area Tumor Institute NCORP, Carle Cancer Center NCORP, Hawaii M/U NCORP

Group 2: University of New Mexico M/U NCORP, Medical University of South Carolina M/U NCORP, Virginia Commonwealth University Massey Cancer Center M/U NCORP, Stroger Hospital of Cook County M/U NCORP, Georgia Cares M/U NCORP

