1.6 Study Design

We plan a multi-site cluster randomized trial using a stepped wedge design with 7 waves. We will recruit 10 clinics for participation. All clinics will begin in the usual care arm. Clinics will be randomized to the timing with which they cross-over to the decision aid intervention, with new clinics crossing over at each wave starting from wave two. Maximizing reach of the decision aid within each clinic is critical for this intervention. We will use the strategy developed in our pilot work to guide implementation;⁵⁴ the process of implementation of the decision aid will occur over a 10-week period during which the clinic does not collect patient-level data. The research team will collect the clinic-level documents that support clinic's implementation efforts for research and take field notes during the implementation process. Data collection within each clinic before and after implementation of the decision aid intervention will be the same; this includes patient surveys and audio recording of the consult. The primary analysis will compare patients in usual care versus the decision aid intervention arms. We will follow the intervention component with patient interviews and focus groups as well as clinic stakeholder focus groups. In this component of the study, we will identify persistent barriers to patient engagement in decision making that could be targeted in future interventions.

We have experienced under-recruitment, in part due to the COVID-19 pandemic. To compensate for the slower accrual, we will extend the period of enrollment for sites that are still recruiting within the stepped wedge design as of 8/30/2021. The extended recruitment beyond Wave 7 would continue for six sites until 12/31/2021. Please see [Section 12.1.3](#) for details.

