12.1 Analysis Plan for Co-Primary Objectives

12.1.1 Primary Analysis

Co-Primary Objective #1: The goal is to evaluate the effectiveness of a decision aid in increasing patient engagement in decision making in clinics serving a high proportion of socioeconomically disadvantaged patients. We will follow an intention to treat approach, using all available data, regardless of group assignment or whether patients viewed the decision aid. The data as collected will have a nested structure: patients nested within surgeons within surgical clinics, this last level being the formal level of intervention. Descriptive analyses will summarize patient, surgeon, and clinic characteristics. When reporting these summary data, we will report as “NR-Not reported” any cell where the number of patients is less than five to avoid inadvertent patient identification. We will test intervention effects in the framework of generalized linear mixed effects models with an “intervention versus usual care” dummy variable (which varies over patients within each surgeon and clinic), a surgeon random effect, and a clinic random effect. Analysis models will include two additional parameters, for wave and wave-squared, respectively to flexibly control for potential time effects and to allow for a non-linear relationship with outcome measures. We will include a post-COVID restart dichotomous variable that reflects whether a patient is enrolled during the post-COVID restart time period for a given site (yes/no). We also will include time (in units of wave) post-COVID in all models. These indicator and time parameters allow for the control of sites restarting the trial post-COVID shut down at different times. This leads to the following planned linear mixed effects model for the two primary outcomes (y) in Aim 1, namely, PEPPi-5 self-efficacy and Active Patient Participation Behaviors:

$$y_{ijk} = \beta_0 + \theta x_{ijk} + \beta_1 t_{1ijk} + \beta_2 t_{1ijk}^2 + \beta_3 z_{ijk} + \beta_4 t_{2ijk} + u_k + u_{j(k)} + e_{i(j(k))}$$

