Here, y_{ijk} denotes the response of the i^{th} level-1 unit (patient) of the j^{th} level-2 unit (surgeon) of the k^{th} level-3 unit (clinic). The variable x_{ijk} ($=0, 1$) denotes the intervention status of patient i from surgeon j within clinic k . The variables t_1 ($=1, 2, 3, 4, 5, 6, 7$) and t_1^2 ($=1, 4, 9, 16, 25, 36, 49$) are the linear and quadratic terms for wave with the corresponding coefficients β_1 and β_2 representing the fixed linear and quadratic effects to model the underlying secular trend. The variable z ($=0, 1$) denotes if patient i was enrolled during the post-COVID restart time period for a given clinic with the corresponding fixed effect coefficient β_3 . The variable t_2 ($=0, 1, 2, 3, 4, 5, 6$) denotes if patient i was enrolled within the first wave post-COVID restart time period ($t_2 = 1$); within the second wave post-COVID restart time period ($t_2 = 2$); and so on through the sixth wave post-COVID restart time period ($t_2 = 6$). The maximum value is $t_2 = 6$ because when the stepped-wedge design was suspended all clinics were at least enrolling part way in wave 2 of the possible 7 waves. For patients enrolled prior to the post-COVID restart time period the value of $t_2 = 0$. The random effect u_k is the level-3 (clinic) random intercept effect (random clinic variance); the random effect $u_{j(k)}$ is the level-2 random intercept effect for

the $j(k)^{th}$ level-2 unit (random surgeon variance nested in clinics); the random effect $e_{i(j(k))}$ is the random individual variance within surgeons nested in clinics. The term β_0 is the intercept. The term θ represents the intervention effect of the decision aid and is the primary effect of interest.

Models will adjust for the a priori specified patient characteristics described above that are likely to be strongly predictive of the endpoints. In the event that the approximately continuous outcomes PEPPi-5 self-efficacy and Active Patient Participation Behaviors are not approximately symmetrically distributed, variable transformation will be considered (e.g., square-root transformation). Further, as part of the planned efficacy analysis we will fully test the variance-covariance structure of the model, while blinded to any treatment effects, which may lead to a more parsimonious model.

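### Clinic randomisation is stratified by a two-level group that the primary model leaves out; adding it is a low-priority consistency fix with a small precision gain for PEPPI-5 only

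*Combined protocol and SAP*

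**What the plan says.** Section 4.7.1 (Stratification) says of the clinic randomisation: "There is one planned composite stratification factor with two levels (group 1; group 2"). It names five sites in each group and says that in forming them "the primary factor considered was whether the site was a minority/underserved NCORP site". It refers to Section 12.0 for the randomisation routine. Section 12 as supplied contains no routine and does not mention the stratification factor.

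Section 12.1.1 (Primary Analysis) sets out the model for both primary endpoints. Its random part is "a surgeon random effect, and a clinic random effect", and the clinic term "is the level-3 (clinic) random intercept effect (random clinic variance"), separate from the patient-level error. For time, "Analysis models will include two additional parameters, for wave and wave-squared, respectively", followed by a post-COVID restart indicator and time since restart. The only further adjustment is this: "Models will adjust for the a priori specified patient characteristics described above". Those are patient characteristics. The stratification group is a property of the clinic, so this sentence does not bring it in.

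Section 1.6 describes a "stepped wedge design with 7 waves. We will recruit 10 clinics for participation". All clinics start in usual care and cross over later.

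**The concern.** A factor that restricts the randomisation would normally appear in the primary model, or the SAP would say why it does not. Here it is absent without comment. If the two groups of clinics differ in mean outcome, that difference is counted as part of the random clinic variance. A fixed group effect would take it out and make the between-clinic part of the comparison more precise.

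Precision matters in this trial. The planned sample fell from 1,050 to 563. With the Wave 1 standard deviations, the detectable effects at 80% power in Section 12.1.2 lie only just below the differences called clinically meaningful: 1.87 against 2 points for PEPPI-5, and 9.6 against 10 for the participation count. With 10 clinics, readers will also ask whether the model matches the randomisation, and that is best settled before results are seen.

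**Working it through.** **Inputs from the documents.** 10 clinics, five crossover steps of two clinics, 7 waves, and one wave per clinic lost to implementation (Sections 1.6, 4.4, 7.1.2, 12.1.3). 563 patients, 23 surgeons, two-sided alpha 0.025 per endpoint (Section 12.1.2). PEPPI-5: SD 3.4, surgeon ICC 0.07, clinic ICC 0.07. Count: SD 19.1, surgeon ICC 0.01, clinic ICC 0.0001.

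**Inputs not in the documents, so assumed.** Accrual by clinic and wave (equal, or random unequal layouts); restart wave per clinic (waves 2 to 5); strata balanced over crossover sequences, except where stated; and the share of clinic variance that the group explains (0 to 100%).

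**Step 1: the plan's own figures.** The detectable effect is (z for alpha + z for power) × SE. For 80% power the multiplier is 2.241 + 0.842 = 3.083; for 90% it is 2.241 + 1.282 = 3.523.
- Implied SE: PEPPI-5 0.55 / 3.083 = 0.178 SD; count 0.50 / 3.083 = 0.162 SD.
- Check at 90% power: 0.55 × 3.523 / 3.083 = 0.628 (stated 0.63); 0.50 × 3.523 / 3.083 = 0.571 (stated 0.57).

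The stated figures agree with each other. They cannot be reproduced exactly, because the accrual projections are not given. Generalised least squares on the stated model gives 0.50-0.52 (PEPPI-5) and 0.45-0.48 (count) with equal accrual. Over random unequal layouts the medians are 0.54 (5th to 95th percentile 0.50-0.60) and 0.49 (0.44-0.56). The stated 0.55 and 0.50 lie inside those ranges.

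**Step 2: add the group.** The same model is refitted with a fixed group effect. The clinic variance is multiplied by (1 − share explained), and the surgeon and patient variances are held fixed. For PEPPI-5, strata balanced:

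| Share of clinic variance explained | Change in SE | Detectable effect, from 0.55 SD | Power for 2 points |
|---|---|---|---|
| 0% | about +0.05% | 0.55 | 85.5% |
| 25% | −0.6 to −0.7% | 0.546 | 85.9% |
| 50% | −1.6% | 0.541 | 86.6% |
| 75% | −3.1% | 0.55 × 0.969 = 0.533 | 87.7% |
| 100% (bound) | −5 to −6% | about 0.52 | about 89% |

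Power is the normal probability of (2/3.4)/SE − 2.241. Without the term this is 0.588/0.178, about 3.30, less 2.241 = 1.06, giving 85.5%.

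In patient terms, a 1.6% smaller SE is worth 1/0.984² − 1 = 3.3%, about 3% more patients.

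**Step 3: the count.** With a clinic ICC of 0.0001 there is almost no clinic variance to explain. The SE is about 0.3% larger on average with the term, and the detectable effect stays at 0.50 SD. If strata are not balanced over sequences, the SE rises by about 2% on average. With unequal accrual as well, the median rise is about 1% and the 95th percentile about 10%.

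**Step 4: the surgeon intercept matters.** Leaving it out gives PEPPI-5 changes of −1.3%, −3.5% and −7.5% at 25%, 50% and 75%, about double those above. With 23 surgeons and a surgeon ICC of 0.07, clinic means still vary through their surgeons, and a clinic-level term cannot remove that part.

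**The case against.** The strongest reply is that the model already handles between-clinic differences. The group is constant within a clinic, so any difference between groups sits in the clinic random intercept. Every clinic is planned to be observed under both conditions, so most of that difference cancels from the within-clinic contrast. This stands, and it is why the gain is small.

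A reader might infer that known differences between the groups are left in the error term. The documents do not support that. They report no outcome difference between the groups, the clinic intercept is separate from patient error, and the group is a composite: one site labelled minority/underserved (Hawaii) is in Group 1. The share of clinic variance explained is therefore an assumption, and it could be zero. A reader might also infer bias or an inflated type I error; nothing in the documents shows either.

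It is tempting to extend the term to the Objective 2 models. No calculation supports that. In the persistent-barrier models the exposure is socioeconomic disadvantage, and a group built mainly on minority/underserved status could absorb part of the association under study.

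Finally, the term is not free for the count. Balance of strata over sequences is also assumed, because the routine that Section 4.7.1 points to is not in Section 12 as supplied.

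**Conclusion.** The inconsistency is real: the randomisation is stratified, the Objective 1 model omits the stratum, and no reason is given. The consequence is minor. The estimate is not biased. The PEPPI-5 standard error could fall by 0 to about 3% if the group explains up to three quarters of the clinic variance, and by 5-6% at most. The count gains nothing. These figures rest on the plan's ICCs, 563 patients, 23 surgeons, assumed accrual and restart patterns, strata balanced over sequences, and normal theory with variances treated as known. The case for the change is agreement with the randomisation; precision is a small bonus. It is a low-priority improvement.

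**What to change.** In Section 12.1.1, add a fixed effect for stratification group (1/2) to the Objective 1 primary model for PEPPI-5 and the participation count. The variable already exists in Section 4.7.1, so the change is one coefficient and one line of the SAP. Do not extend it to the Objective 2 models on this argument.

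The cost is one clinic-level degree of freedom out of 10 clinics, and a slightly larger standard error for the count: about 0.3%, or a few percent if strata turn out to be unbalanced over the crossover sequences.
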